5. DATA HANDLING CONVENTIONS

All data collected in the study will be listed, excluding actigraphy data or data collected on the Handheld Device.

5.1 General Data Reporting Conventions

Continuous variables will be summarized using the following descriptive statistics: number of subjects, mean, median, standard deviation, standard error, minimum, and maximum. Unless specified otherwise, means, medians, and confidence intervals will be presented to one more decimal place than the raw data, and the standard deviations and standard errors will be presented to two more decimal places than the raw data.

Categorical and count variables will be summarized by the number of subjects and the percent of subjects in each category. Categories with zero counts will not have zero percentages displayed. Percentages will be presented with one decimal place.

Duration in months will be calculated as ([the number of days / 365.25] *12).

Unless specified otherwise, all statistical tests will be 2-sided hypothesis tests performed at the significance level of 5% for main effects and all confidence intervals will be 2-sided 95% confidence intervals. P-values will generally be presented to 4 decimal places; values less than 0.0001 will be presented as <0.0001.

5.2 Derived Efficacy Variables

In general, assessment total scores and subscores will be derived within the analysis datasets. In the event that total scores and/or subscores are also collected on the electronic case report from (eCRF), the derived values will be used for all analyses. Both the raw and derived scores will be presented in listings.

5.2.1 Mini-Mental State Examination (MMSE)

MMSE is assessed at Screening. The MMSE is an 11-area, 30 items questionnaire that is used to measure cognitive impairment, with lower scores indicating more severe cognitive impairment. The total score (0-30) is calculated as the sum of the 30 item scores. The total score will be missing if there are at least one missing items. The MMSE is being used in this study to screen for cognitive impairment.

5.2.2 Neuropsychiatric Inventory (NPI)

For subjects enrolled under the Original Protocol or Protocol Amendments 1 or 2, the NPI is assessed at Screening. At least one of the following domains must have a Frequency×Severity greater than or equal to 3: Domain A Delusions, Domain B Hallucinations, Domain D

Depression/Dysphoria, Domain G Apathy/Indifference, Domain H Disinhibition, or Domain I Irritability/Lability. The NPI was removed from the list of assessments in Protocol Amendment 3.

Domain scores will not be derived. Scores, as reported in RAVE, will be listed.

5.2.3 Patient-Reported Outcomes Measurement Information System (PROMIS®)

Data will be collected by the Handheld Device and the analysis method will not be covered by this SAP.

5.2.4 Sleep-Related Impairment Scale

Data will be collected by the Handheld Device and the analysis method will not be covered by this SAP.

5.2.5 Nighttime Sleep Scale

Data will be collected by the Handheld Device and the analysis method will not be covered by this SAP.

5.2.6 Trail Making Test (TMT) Parts A and B

The TMT is a neuropsychological test of visual attention and task switching. The TMT has two parts, Parts A and B. Part A measures rote memory and consists of 25 circles on a piece of paper with the numbers 1-25 written randomly in the circles. The subject is to connect the circles in numerical order. Part B measures executive functioning and consists of 24 circles on a piece of paper, half of the circles have the numbers 1-12 in them and the other half (12) contain the letters A-L. The subject must alternate connecting circles with numbers and circles with letters. Time to completion or maximum time (seconds) for Parts A and B are recorded. The maximum completion time for Part A is 150 seconds, and 300 seconds for Part B. Higher completion or maximum time denote slower visual attention and task switching. Missing values will not be imputed.

5.2.7 Hopkins Verbal Learning Test-Revised (HVLT-R)

The HVLT is a brief verbal learning and memory test with six alternate forms. The HVLT is ideal in situations calling for repeated neuropsychological examinations, but it lacks a delayed recall trial which is essential for the assessment of abnormal forgetting and therefore the revised version of the HVLT (HVLT-R) was developed. The HVLT-R test consists of three trials of free-recall of a 12-item, semantically categorized list, followed by yes/no recognition. Approximately 20-25 min later, a delayed recall trial (trial 4) and a delayed recognition trial are completed.

Total recall will be derived as the sum of total correct responses for Trials 1, 2, and 3. Total recall will be set to missing if all 3 trials are not completed.

Retention (%) will be derived as $(\text{Trial 4 score} \div \text{Higher score of Trials 2 and 3}) \times 100$.

The Delayed Recognition Trial will be used to derive the recognition discrimination index, which will be calculated as the total number of true-positive responses minus the total number of false-positive errors (ranging from -12 to 12). Higher indexes denote better verbal learning and memory test results. Missing total numbers of true-positive responses and/or false-positive errors will not be imputed. The index will be missing if total number of true-positive responses and/or total number of false-positive errors are missing.

5.2.8 Parkinson's Disease Non-motor Symptoms (PD NMS) Questionnaire

The Non-motor Symptoms questionnaire is a validated, clinician rated questionnaire that assesses non-motor issues that may be present in Parkinson's disease. The PD NMS is comprised of 30 items grouped into nine domains: cardiovascular including falls, sleep/fatigue, mood/cognition, perceptual problems/hallucinations, attention/memory, gastrointestinal tract, urinary, sexual function, and miscellaneous.

Each item is scored with respect to frequency (1=rarely, 2=often, 3=frequent, 4=very frequent) and severity (0=none, 1=mild, 2=moderate, 3=severe). Individual item scores are calculated as frequency \times severity scores. The total score, ranging from 0 to 360, is calculated as the sum of the 30 item scores. Higher total scores denote worse non-motor symptoms. If 6 or fewer item scores are missing, then the total score will be imputed as the mean of the non-missing item scores multiplied by 30 and rounded to the nearest integer. The total score will be missing if there are at least 7 missing item scores. Missing item scores will not be imputed.

5.2.9 Patient Global Impression – Improvement (PGI-I)

The PGI-I is a global index used to rate the response of a condition to a therapy. The PGI-I asks the patient to rate their symptoms now, as compared with how it was at Baseline before beginning treatment. Severity ratings ranging from 1 to 7 are based on the behavioral domain(s) of clinical concern:

1 = Very much better	4 = No change
2 = Much better	5 = A little worse
3 = A little better	6 = Much worse
	7 = Very much worse

Higher PGI-I scores denote worse symptoms compared with Baseline before beginning treatment. Missing PGI-I scores will not be imputed.

Beginning with Protocol Amendment 3, rather than being assessed on a single global scale as described above, subjects were assessed on the following symptom-specific PGI-I scales:

delusions, hallucinations, depression/dysphoria, apathy/indifference, disinhibition, irritability/lability. For those subjects assessed with symptom-specific CGI-I scales, a single, global score will be derived by taking the arithmetic mean of the non-missing symptom-specific scores at the given visit, rounded to the nearest integer.

5.2.10 Clinical Global Impression – Severity (CGI-S)

The CGI-S scale is a clinician-rated, 7-point scale that is designed to rate the severity of the subject's neuropsychiatric symptoms at the time of assessment using the Investigator's judgment and past experience with subjects who have the same disorder. The CGI-S will be assessed at Screening and at Baseline. Severity ratings ranging from 0 to 7 are based on the behavioral domain(s) of clinical concern used for eligibility:

0 = Not assessed	4 = Moderately ill
1 = Normal, not at all ill	5 = Markedly ill
2 = Borderline ill	6 = Severely ill
3 = Mildly ill	7 = Among the most extremely ill patients

Higher CGI-S scores denote more severe illness. Missing CGI-S scores will not be imputed.

Beginning with Protocol Amendment 3, rather than being assessed on a single global scale as described above, subjects were assessed on the following symptom-specific CGI-S scales: delusions, hallucinations, depression/dysphoria, apathy/indifference, disinhibition, irritability/lability. For those subjects assessed with symptom-specific CGI-S scales, a single, global score will be derived by taking the arithmetic mean of the non-missing symptom-specific scores at the given visit, rounded to the nearest integer.

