4.1 Inclusion Criteria

A subject must meet all of the following inclusion criteria to be eligible for participation in the study:

1. Male or female subjects 50 to 85 years of age, inclusive, at Screening and Baseline
2. Can understand the nature of the trial and protocol requirements and provide written informed consent
3. Is able to demonstrate the ability to complete subject-reported outcome measures on a handheld device, is willing to wear a data capture instrument (e.g., an actigraph), and can be reliably rated on assessment scales (in the opinion of the Investigator)
4. Can designate an “informant” (a relative, housemate, or friend) who the subject agrees can provide reliable information on the subject’s well-being and is willing to attend clinic visits with the subject
5. Is able to swallow the test capsule without difficulty during the Screening visit
6. Has a Mini-Mental State Examination (MMSE) score ≥ 19

7. Has a diagnosis of idiopathic Parkinson's disease, without any other known or suspected cause of parkinsonism, according to the UK Parkinson's Disease Society Brain Bank Clinical Diagnostic Criteria ([Hughes et al. 1992](#)). Initial diagnosis of PD must have been made more than 1 year prior to Screening.
8. [Inclusion criterion eliminated]
9. Has at both Visit 1 (Screening) and Visit 2 (Baseline), a CGI-S score of ≥ 3 on at least one of the following non-motor neuropsychiatric symptoms that warrant treatment with an antipsychotic agent based on Investigator judgement. Such symptoms do not need to be the same at Screening and Baseline, and all symptoms should be assessed at both Screening and Baseline.
 - a. Delusions
 - b. Hallucinations
 - c. Depression/Dysphoria
 - d. Apathy/Indifference
 - e. Disinhibition
 - f. Irritability/Lability
10. If the subject is on anti-Parkinsonian medication, they must be on a stable regimen for 1 month prior to Baseline and not planning (at the time of the Baseline visit) to make a major change in dose(s)
11. If the subject has had stereotaxic surgery for subthalamic nucleus deep brain stimulation, they must be at least 6 months post-surgery. The stimulator settings must have been stable for at least 1 month prior to the Baseline visit and are expected to remain stable during the trial.

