12.2 Adjustment for Covariates

The corresponding baseline value will be included as a covariate for the analysis of time to completion or maximum time of TMT Parts A and B, HVLT-R recognition discrimination index, and PD NMS total score. Baseline CGI-S score will be used as a covariate for the CGI-I analysis.

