13. METHODS OF EFFICACY ANALYSES

The change from Baseline in the exploratory efficacy endpoints measured at scheduled visits including time to completion or maximum time of TMT Parts A and B, HVLT-R recognition discrimination index, and PD NMS total score will be analyzed using an analysis of covariance model (ANCOVA) using observed scores. The model will include treatment group as a factor and the corresponding Baseline measure as a covariate.

Summary statistics (observed and change from Baseline), LS means, the between-group differences (Pimavanserin – Placebo and Quetiapine – Placebo) in LS means with the corresponding 95% confidence intervals, p-values, and the effect sizes (Cohen's d) will be presented at each post-Baseline visit for the Exploratory Analysis Set.

CGI-I score will be analyzed using a similar ANCOVA model with treatment group as a factor and Baseline CGI-S score as a covariate.

PGI-I score will be analyzed using an analysis of variance model with treatment group as a factor.

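### From Amendment 3 the Baseline CGI-S covariate is a rounded mean over all six symptoms, so for a subject with one qualifying symptom it barely reflects that symptom's severity

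*SAP*

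**What the plan says.** **Entry.** Inclusion criterion 9 (Protocol 4.1) asks for a CGI-S of 3 or more "on at least one of the following non-motor neuropsychiatric symptoms that warrant treatment with an antipsychotic agent". It names six symptoms and adds that "all symptoms should be assessed at both Screening and Baseline".

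**Scoring.** SAP 5.2.10 says that from Amendment 3 CGI-S is rated per symptom, "rather than being assessed on a single global scale as described above". The single score is then "derived by taking the arithmetic mean of the non-missing symptom-specific scores at the given visit, rounded to the nearest integer". SAP 5.2.9 and 5.2.11 apply the same rule to PGI-I and CGI-I.

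**Basis of the ratings.** For the single scale, SAP 5.2.10 states: "Severity ratings ranging from 0 to 7 are based on the behavioral domain(s) of clinical concern used for eligibility". SAP 5.2.11 says the same for CGI-I. Protocol 6.2.6 and 6.2.7 also tie the PGI-I and CGI-I ratings to the symptoms used for eligibility.

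**Use.** SAP 12.2: "Baseline CGI-S score will be used as a covariate for the CGI-I analysis". SAP 13: "CGI-I score will be analyzed using a similar ANCOVA model with treatment group as a factor and Baseline CGI-S score as a covariate", and "PGI-I score will be analyzed using an analysis of variance model with treatment group as a factor".

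**The concern.** The derivation departs from the stated basis of the ratings. A subject can enter on one troublesome symptom, yet the covariate averages it with five others that may be absent or borderline, and then rounds. A mildly ill and an extremely ill subject can end up with the same value, or one point apart.

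Baseline CGI-S is the only adjustment in the CGI-I model. If it hardly varies with the severity of the treated symptom, it removes little residual variance. With at most 11 subjects in three arms, the ANCOVA has at most 11 − 3 − 1 = 7 residual degrees of freedom, so a weak covariate is not free.

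Two further effects are conditional. If single global ratings from before Amendment 3 are also analysed, the covariate mixes two kinds of score. And if sites rated non-qualifying symptoms on CGI-I or PGI-I, the endpoint itself may be pulled away from the change in the treated symptom.

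**Working it through.** The plan gives no worked score to reproduce, so the check applies its rule directly.

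**Inputs.** Six symptoms; CGI-S 1 = normal, 2 = borderline, entry at 3 or more, maximum 7 (SAP 5.2.10, Protocol 4.1); CGI-I and PGI-I 4 = no change (SAP 5.2.9, 5.2.11). The SAP does not say how ties are rounded, so half-up is used and half-to-even is the check.

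**1. One qualifying symptom at s, the other five at 1.** Mean = (s + 5)/6.

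| s | mean | rounded (both tie rules) |
|---|---|---|
| 3 | 1.33 | 1 |
| 4 | 1.50 | 2 |
| 5 | 1.67 | 2 |
| 6 | 1.83 | 2 |
| 7 | 2.00 | 2 |

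**2. The other five at any mix of 1 and 2.** With j of them at 2, mean = (s + 5 + j)/6, for s = 3 to 7 and j = 0 to 5: 30 profiles.
- Half-up: 2 in 23, 3 in 6 (s = 5 with j = 5; s = 6 with j of 4 or 5; s = 7 with j of 3 to 5), and 1 in one (s = 3, j = 0).
- Half-to-even: 2 in 26, 3 in 3, 1 in one.
- At s = 3 or 4 the largest means are 13/6 = 2.17 and 14/6 = 2.33, so the score never reaches 3.

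**3. What rounding adds.** This is the squared correlation of the derived score with s. The weights are equal, which is illustrative only.
- Others at 1: the unrounded mean is linear in s, so R² = 1.00. For the rounded score the sum of cross-products is 2.0 and the sums of squares are 10 and 0.8, so R² = 2.0²/(10 × 0.8) = 0.50.
- All 30 profiles, unrounded: the variances of s and j are 2 and 2.92, so R² = 2/4.92 = 0.41.
- All 30 profiles, rounded half-up: cross-products 10, sums of squares 60 and 6.17, so R² = 100/(60 × 6.17) = 0.27.

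Averaging and rounding therefore each lose information.

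**4. Several symptoms raised, the rest at 1.** Three at 4: (12 + 3)/6 = 2.50, which is 3 half-up. Two at 6: (12 + 4)/6 = 2.67, which is 3. Four at 5: (20 + 2)/6 = 3.67, which is 4. These subjects spread further.

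**5. Mixed scales.** Assume that a global rating from before Amendment 3 equals the qualifying symptom's severity. Ratings of 3, 4, 5, 6, 7 then stand beside derived scores of 1, 2, 2, 2, 2 from step 1: gaps of 2, 2, 3, 4 and 5 points.

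**6. CGI-I and PGI-I.** One qualifying symptom rated q.
- Other five rated 4: (q + 20)/6 = 3.50, 3.67, 3.83 for q = 1, 2, 3. All become 4, no change.
- Other five missing: the score is q.
- CGI-I only, five codes of 0 averaged as scores: q/6 is 0.50 to 1.17 for q = 3 to 7, which rounds half-up to 1, very much improved.

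**The case against.** The strongest reply is that little hangs on this. A weak baseline covariate does not bias a randomized comparison. The trial stopped at 11 randomized subjects (SAP 19), the endpoints are exploratory with no multiplicity adjustment (SAP 12.4), and raw scores are listed (SAP 5.2). Amendment 3 is dated 31 January 2020 and enrollment halted in March 2020, so few subjects may have been rated on six scales. All of this stands, and it sets the severity.

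The profiles are also chosen. Criterion 9 says at least one symptom, and it requires the investigator to judge that the symptom warrants antipsychotic treatment, so other symptoms can score 3 or more without being the target. One at 5, three at 3 and two at 1 gives 16/6 = 2.67, which is 3. A reader might infer that the covariate is nearly constant in the analysed sample. The documents do not support that, because they do not give the mix of subjects.

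A reader might also infer that CGI-I and PGI-I are certainly diluted, or diluted only when the other symptoms were rated 4. Neither follows. The protocol does not require all six symptoms to be rated on these scales. Ratings left missing do no harm, while any rating that differs from the qualifying one (3 or 5, for example) moves the mean.

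One could argue that a global score should average every symptom. That does not fit the eligibility basis in SAP 5.2.10 and 5.2.11, and even an all-symptom average does not need rounding for an ANCOVA or ANOVA.

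**Conclusion.** The point holds for the CGI-S covariate. For subjects rated on six scales with one symptom at 3 to 7 and the other five at 1 or 2, the stated rule gives 2 in 23 of 30 profiles and otherwise 1 or 3, so the covariate barely tracks the severity of the symptom being treated. Rounding worsens this: R² falls from 1.00 to 0.50 with the others at 1, under equal weights that describe no documented population.

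The consequence is mainly lost precision in one exploratory analysis. The mixing of scales arises only if single global ratings are analysed as well, and the effect on CGI-I and PGI-I depends on site practice that the documents leave open. Severity is minor. Confidence is high in how the rule behaves and low in how much it changed any result here.

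**What to change.** 1. **Drop the rounding** for the derived CGI-S, CGI-I and PGI-I scores. The small cost is fractional scores beside integer single-scale ratings. This step alone does not remove the scale mix: with the others at 1, unrounded scores still run only from 1.33 to 2.00.

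2. **Derive Baseline CGI-S, CGI-I and PGI-I from the eligibility symptoms**, for example those with Baseline CGI-S of 3 or more. This set is a proposal, since criterion 9 also rests on investigator judgement. It contains at least one symptom for every subject rated on six scales who met the criterion at Baseline. Report the unrounded all-symptom mean as supportive, so that symptoms that qualified only at Screening or emerged later are not lost. For a subject with only a global Baseline CGI-S, keep that rating as the covariate; if later visits used symptom scales, take the eligibility symptoms from the recorded Screening NPI domain scores (SAP 5.2.2). The cost is one stated symptom set, one supportive summary and a few lines of derivation code on data already collected.

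3. **Housekeeping.** State that code 0 (not assessed) is missing for CGI-S and CGI-I. In the derivation sentence of SAP 5.2.9, replace CGI-I with PGI-I.

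The SAP is dated 19 October 2020 and the documents give no unblinding date. If treatment codes are already released, report the revised derivation as a labelled sensitivity analysis.

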5.2.11 Clinical Global Impression – Improvement (CGI-I)

The CGI-I is a clinician-rated, 7-point scale that is designed to rate the improvement in the subject's symptoms at the time of assessment, relative to the symptoms at Baseline. Severity ratings ranging from 0 to 7 are based on the behavioral domain(s) of clinical concern used for eligibility:

0 = Not assessed	4 = No change
1 = Very much improved	5 = Minimally worse
2 = Much improved	6 = Much Worse
3 = Minimally improved	7 = Very much worse

Higher CGI-I scores denote less improvement in illness. Missing CGI-I scores will not be imputed.

Beginning with Protocol Amendment 3, rather than being assessed on a single global scale as described above, subjects were assessed on the following symptom-specific CGI-I scales: delusions, hallucinations, depression/dysphoria, apathy/indifference, disinhibition, irritability/lability. For those subjects assessed with symptom-specific CGI-I scales, a single, global score will be derived by taking the arithmetic mean of the non-missing symptom-specific scores at the given visit, rounded to the nearest integer.

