6.2.7 Clinical Global Impression - Improvement

The CGI-I is a clinician-rated, 7-point scale that is designed to rate the improvement in the subject's non-motor neuropsychiatric symptoms at the time of assessment, relative to the symptoms at Baseline ([Guy 1976](#)).

Severity ratings should be based on the neuropsychiatric symptom(s) of clinical concern used for eligibility.

This clinician-administered assessment is to be completed at the clinic visits indicated in [Table S-1](#).

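### SAP 5.2.10 and 5.2.11 put a not-assessed code of 0 inside the CGI-S and CGI-I rating range and do not exclude it from the averaged score

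*SAP*

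**What the plan says.** SAP 5.2.11 calls CGI-I a seven-point scale and then lists eight codes: "Severity ratings ranging from 0 to 7 are based on the behavioral domain(s) of clinical concern used for eligibility". The lowest code is "0 = Not assessed", and the next is "1 = Very much improved". On direction and missing data it says: "Higher CGI-I scores denote less improvement in illness. Missing CGI-I scores will not be imputed".

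From Amendment 3 onward, six symptom scales replace the single global rating. The global score is then the "arithmetic mean of the non-missing symptom-specific scores at the given visit", rounded to an integer. SAP 5.2.10 has the same 0 code and the same averaging rule for CGI-S. By contrast, SAP 5.2.9 gives PGI-I a range of 1 to 7 with no 0 code.

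On what is rated, Protocol 6.2.7 says: "Severity ratings should be based on the neuropsychiatric symptom(s) of clinical concern used for eligibility". Under inclusion criterion 9 (Protocol 4.1), one symptom with a CGI-S of at least 3 is enough for entry, and all symptoms should be assessed at both Screening and Baseline.

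SAP 13 analyses CGI-I by ANCOVA with Baseline CGI-S as covariate. SAP 12.3 says that missing efficacy data are not imputed. Neither section mentions code 0.

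**The concern.** A 0 that has been entered is a recorded value, and the SAP places it inside the rating range. On the ordinary meaning of non-missing, a programmer would keep it. Lower CGI-I is better, so an unrated symptom would then count as a better result than the best real rating.

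The derived score would depend partly on how many symptoms were rated, and not only on how the subject changed. It would also be modelled together with single global ratings from subjects enrolled before Amendment 3, which are not averaged. For those subjects a single global score recorded as 0 would enter the analysis directly.

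On the CGI-S side, SAP 5.3 defines Baseline as the last non-missing value before dosing. A global CGI-S of 0 at the Baseline visit could therefore displace a valid Screening score as the covariate.

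**Working it through.** The plan states no figure on this point, so there is none to reproduce. The check applies the SAP's derivation directly.

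**Inputs**
- Six symptom scales (SAP 5.2.11).
- Codes 0 to 7, with 0 for not assessed and 1 as the best rating (SAP 5.2.11).
- Rounded mean of non-missing scores, with no rule removing 0 (SAP 5.2.11).
- Minimum of one qualifying symptom (Protocol 4.1, criterion 9).
- Assumption: exact halves round up. The SAP gives no tie rule.

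**Zeros kept.** If m symptoms all have rating s and the other 6 − m are coded 0, the mean is m × s / 6. The rounded global scores are:

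| Symptoms rated (m) | s=1 | s=2 | s=3 | s=4 | s=5 | s=6 | s=7 |
|---|---|---|---|---|---|---|---|
| 1 | 0 | 0 | 1 | 1 | 1 | 1 | 1 |
| 2 | 0 | 1 | 1 | 1 | 2 | 2 | 2 |
| 3 | 1 | 1 | 2 | 2 | 3 | 3 | 4 |
| 4 | 1 | 1 | 2 | 3 | 3 | 4 | 5 |
| 5 | 1 | 2 | 3 | 3 | 4 | 5 | 6 |
| 6 | 1 | 2 | 3 | 4 | 5 | 6 | 7 |

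Examples:
- One symptom rated no change: 4/6 = 0.67, scored 1.
- One symptom rated 5, 6 or 7 (worse): 0.83, 1.00 or 1.17, each scored 1, very much improved.
- One symptom rated 1 or 2 (real improvement): 0.17 or 0.33, each scored 0, which is the not-assessed code itself.
- Two symptoms rated 6: 12/6 = 2, much improved.

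If every rated symptom is worse (any mix of 5, 6 and 7), the global score is 1 with one rated, 2 with two, 3 to 4 with three, 3 to 5 with four, 4 to 6 with five, and 5 to 7 with all six. Only the last row of the table is free of distortion.

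**Zeros set to missing.** The mean becomes the sum of the rated codes divided by m. If every rated symptom is 5 or more, the global score is at least 5 for every m.

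**CGI-S.** One symptom rated 3 to 7 with five zeros gives 0.50 to 1.17, which rounds to 1, the normal category. This needs five symptoms left unassessed at entry, contrary to criterion 9.

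**Effect on an arm mean.** Arm sizes are not given. Assume 3 or 4 subjects per arm (11/3 = 3.67). One subject moved from 6 to 1 then shifts the unadjusted arm mean by 5/4 = 1.25 to 5/3 = 1.67 points.

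**The case against.** The best defence is that 0 was never meant as a score. A symptom labelled not assessed has no assessment, so non-missing may have been intended to exclude it. The seven-point description and the seven substantive anchors support that. A dataset or programming specification outside these documents may already recode it. This stands as a statement of probable intent, but it does not repair the text. The SAP gives explicit missing-item rules for MMSE (5.2.1), HVLT-R (5.2.7), PD NMS (5.2.8) and the MDS-UPDRS subitems (14.6), and none for this code. Where it defers derivation rules to another document, as in 5.3.2, 5.4 to 5.6 and 5.9, it says so. Here it does not. It also does not treat every unperformed assessment as missing, since 14.5 tabulates physical examinations not done as a result category.

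A second defence is that zeros may be few. This stands in part. Protocol 6.2.7 bases ratings on the eligibility symptoms but does not say that only those are to be rated, and SAP 5.2.11 says subjects were assessed on all six scales. A reader might infer that five zeros per subject were the normal entry, but the documents do not establish that. They make zeros foreseeable: one symptom suffices for entry, the request to assess all symptoms covers Screening and Baseline only, and a not-assessed code exists.

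A reader might also infer that the CGI-S covariate is affected to the same degree. The text of 5.2.10 has the same flaw, but CGI-S is collected only at Screening and Baseline, where criterion 9 asks for all symptoms. Zeros there would mostly reflect departures from the protocol.

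Finally, SAP 5.2 lists raw scores beside derived ones, so a careful reader could detect a mis-derived value. That helps detection, but it does not correct the model.

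**Conclusion.** The derivation is wrong as written. Followed literally, SAP 5.2.11 counts an unassessed symptom as a better outcome than the best real rating. In the extreme pattern of one symptom rated and five coded 0, every rating from 4 to 7 becomes 1. With two rated 6 and four coded 0, the score is 2. The distortion shrinks as more symptoms are rated and is nil when all six are.

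This rests on a recorded 0 counting as non-missing and on zeros occurring in post-baseline CGI-I. The first is the literal reading; the second is foreseeable but not shown. The documents do not support the stronger inference that worsening subjects were in fact scored as very much improved.

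The reach is limited. CGI-I is exploratory, SAP 19 reports 11 subjects randomized, and averaging applies only to those assessed on the symptom-specific scales. That number is not given; Amendment 3 is dated 31 January 2020 and enrollment was halted in March 2020 (SAP 1 and 3.6). The primary endpoint, treatment-emergent adverse events, is unaffected. The change is still worth making, because SAP 13 reports least-squares means, confidence intervals, p-values and effect sizes for this score, and in so small a trial one mis-scored subject can move an arm mean by more than a point under the arm sizes assumed above.

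**What to change.** In SAP 5.2.10 and 5.2.11:
- State the rating range as 1 to 7 and describe 0 as a collection code for a symptom not assessed.
- Set code 0 to missing before averaging, before selecting the baseline value and before modelling. Apply this also to a single global CGI-S or CGI-I recorded as 0.
- Set the global score to missing if no symptom was rated at that visit.
- Keep the recorded code in the raw data listings, so that SAP 5.2 is still met.

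The cost is a short text change in each of two subsections and one recode line in the derivation. No new data are needed. The downside is that a visit with no rated symptom becomes missing and drops out of the observed-case analysis.
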